2/2/2015

Title: Mucosal impedance in eosinophilic esophagitis and the effect of treatment

Co-Principal Investigator: [name] and [name] MD

Co-Investigators: [REDACTED]

Study Coordinators: [REDACTED]
[REDACTED]

Background:

Eosinophilic esophagitis (EoE) is a chronic disease characterized by esophageal eosinophilia leading to inflammation and fibrosis in response to food antigens. One of the presumptions in this disease is that antigen recognition occurs in the esophagus by dendritic cell recognition and generation of a TH2 allergic response. Although it is speculated that the esophageal epithelium increases its permeability to allow for antigen penetration, this is not well proven.

Mucosal impedance reflects the ability of electric current to flow between two sensors while in contact with the epithelium. An increase in current flow is presumably due to an increase in ions and water crossing the membrane, which are good conductors of electricity. Through this technique an overall measure of “leakiness” of the esophageal epithelium is obtained. This increased permeability may reflect epithelial destruction as in erosive esophagitis, a change in epithelium from squamous to columnar as in Barrett’s esophagus or in conditions in which there are dilated intercellular spaces as has been observed in both gastroesophageal reflux and eosinophilic esophagitis.

While standard diagnostic evaluation for EoE includes upper endoscopy with esophageal biopsies, assessment of mucosal impedance is not. Recently, a new technology has emerged allowing for direct assessment of mucosal impedance at the time of routine upper endoscopy. Yuksel and colleagues have described use of a 2mm diameter single-channel catheter used during the time of EGD which demonstrated lower mucosal impedance in areas of erosive esophagitis and in the mucosa of patients with nonerosive reflux disease compared to healthy controls.¹ In the same manner, mucosal impedance may be lower in patients with EoE, allowing for submucosal antigen exposure and the characteristic Th2 response.

Hypothesis:

Patient with eosinophilic esophagitis have diminished mucosal impedance, reflecting increased permeability to allergens occurring at least in the esophagus and possibly in the buccal mucosa.

Primary Aim:

1. Assess mucosal impedance in patients with EoE of both the esophageal and buccal mucosa.

Secondary Aim:

2. Changes in mucosal impedance in patients with EoE following treatment

Methods:

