Study Design:

Patients referred to the Mayo Clinic Rochester either with an establish or suspected diagnosis of EoE will be identified. Those scheduled for clinically indicated upper endoscopy for esophageal biopsies either for initial diagnosis or activity assessment of EoE will be studied. After investigation of established or suspected EoE, a total of 75 patients with confirmed EoE patients. In addition, patients undergoing clinically indicated upper endoscopy for indications either than gastroesophageal reflux or dysphagia will be studied as controls. A total of 10 control patients will be studied.

Inclusion criteria:

- Adults ages 18-90 undergoing clinically indicated upper endoscopy
- Patients with EoE, defined as dysphagia with histologic finding of greater than or equal to 15 eosinophils per high powered field on esophageal biopsy despite at least 6 weeks of twice daily proton pump inhibitor therapy
- Patients undergoing clinically indicated upper endoscopy for indications other than dysphagia or GERD with normal appearing esophageal mucosa.

Exclusion criteria:

- Medical conditions such as severe heart or lung disease that preclude safe performance of endoscopy
- Patients with conditions known to be associated with esophageal eosinophilia, including Crohn's disease, Churg-Strauss, achalasia, and hypereosinophilic syndrome
- Inability to read due to: Blindness, cognitive dysfunction, or English language illiteracy

Study Flow:

Patient undergoing clinically indicated endoscopy and esophageal biopsies for diagnosis or assessing activity of eosinophilic esophagitis will be identified. In addition, patients undergoing

clinically indicated upper endoscopy for indications other than dysphagia or GERD will be identified:

1. Before commencing the procedure, a baseline impedance will be obtained by asking the patient to hold the end of the probe against his/her buccal mucosa for 1 minute for an initial reading.
2. Clinically indicated endoscopic exam will be completed
3. On withdrawal of the upper endoscope into the esophagus, a 2.13mm mucosal impedance catheter (Figure) will be passed through the channel of the standard upper endoscope.
4. The probe will be placed on the esophageal mucosa 5cm above the gastroesophageal junction for 5 seconds and recordings obtained.
5. In patients with suspected or established EoE in whom clinically indicated esophageal biopsies are indicated, 2 biopsies will then be obtained at this level.

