6. The scope will then be withdrawn to 10 and 20 cm above the gastroesophageal junction and the same procedure including biopsies performed respectively.
7. In total, six biopsies will be taken which is part of the guideline recommended protocol for eosinophilic esophagitis for clinical purposes.
8. Biopsies in patients undergoing clinically indicated upper endoscopy for indications other than GERD or dysphagia in whom biopsies are not ordered will undergo the same protocol, except esophageal biopsies will not be obtained.

There is minimal risk associated with this study. Upper endoscopy carries an approximate 1 in 3,000 risk of perforation, bleeding, and infection. As this is a clinically indicated study, there is no increased risk from the standpoint of endoscopy for enrolled patients. The impedance catheter measures only 2.13mm in diameter and is flexible with a blunt end. Given the catheter size and the fact that it is passed with direct endoscopic visualization, risk of complications such as perforation or bleeding are minimized and are essentially no different than standard EGD with esophageal biopsies. In fact, in the initial description of use of this catheter 69 patients were studied with no catheter associated complications were reported.¹ In addition, as impedance recording requires on average 5 seconds per level to complete, the protocol will lengthen the procedure time on average 15 seconds which will not have clinically relevant implications regarding need for conscious sedation and procedure related risk. There are no additional risks to the subject adding the buccal mucosal impedance testing.

Impedance testing

Statistical Analysis:

[figure not shown]
As a pilot, ten patients will be studied before and after treatment for eosinophilic esophagitis. This number of patients will be increased if there are treatment failures until there is a total of ten effectively treated patients studied. Effective treatment is defined by the elimination of esophageal eosinophilia on follow up endoscopic biopsy. Ten control patients without esophageal disease will be studied.

Primary Endpoint:

1. Mean and median mucosal impedance in patients with EoE patients compared to controls

Secondary Endpoints:

2. Maximal mucosal impedance in EoE patients compared to minimal mucosal impedance in control patients to determine a potential diagnostic cutoff value
3. Mean and median mucosal impedance in EoE patients post treatment in comparison to pretreatment

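### Does recruiting until ten histologic responders make the before/after impedance change in treated EoE patients misleading?

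*Combined protocol and SAP*

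**What the plan says.** The Statistical Analysis section opens with a count of patients: "As a pilot, ten patients will be studied before and after treatment for eosinophilic esophagitis". It then gives an extension rule, "This number of patients will be increased if there are treatment failures until there is a total of ten effectively treated patients studied", and defines success by histology: "Effective treatment is defined by the elimination of esophageal eosinophilia on follow up endoscopic biopsy". The only comparison group is described as "Ten control patients without esophageal disease will be studied".

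Two places say what the series is for. The Secondary Aim is "Changes in mucosal impedance in patients with EoE following treatment". Item 3 under Secondary Endpoints is "Mean and median mucosal impedance in EoE patients post treatment in comparison to pretreatment". Neither is limited to responders, and nothing in the document says that failures' readings are discarded. Nor does it say that they are included: no analysis set is named for item 3. The title speaks of "Mucosal impedance in eosinophilic esophagitis and the effect of treatment".

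**The concern.** A series that closes on its tenth success invites an analysis of those ten successes. That analysis would condition on an outcome seen only after treatment. It would describe how impedance changes when eosinophilia clears, which is a different question from how impedance changes in treated patients. The protocol's hypothesis links low impedance to EoE, so patients whose eosinophilia persists would be expected to recover less. A responder-only figure reported as the change following treatment would then be too large. With the analysis set unnamed, the choice could in principle be made after the data are seen.

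A second worry is that the title names an effect of treatment while no untreated EoE group is studied.

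**Working it through.** **Nothing to reproduce.** The plan gives no significance level, power, standard deviation, response rate or expected impedance change for the ten. The ten and the stopping rule come from Statistical Analysis. The response rates and relative changes below are assumptions, shown over a range, with one treatment course per patient and everyone returning for follow-up.

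**Step 1: which patients does the text point to?** The opening sentence counts patients studied before and after treatment. The extension rule increases that same number when treatments fail. Failures are therefore part of the enlarged series, not replaced in it. The Secondary Aim and item 3 refer to EoE patients after treatment without qualification. The responder count decides when recruitment ends; it does not decide who is analysed.

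**Step 2: size if only responders were analysed.** Let p be the response rate and f the failures' mean change divided by the responders'. With the responders' mean change set to 1, the all-treated mean is p + (1 − p)f, so the ratio of responder-only to all-treated change is 1/[p + (1 − p)f]. For example, p = 0.5 and f = 0.5 give 1/(0.5 + 0.25) = 1.33.

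**Step 3: size if all treated patients are analysed.** Recruitment ends on a responder, so the observed responder share 10/N averages slightly above p. N, the total treated, has probability C(n − 1, 9) p^10 (1 − p)^(n − 10) and mean 10/p. With s = E[10/N], the expected all-treated result divided by its true value is [s + (1 − s)f]/[p + (1 − p)f]. At p = 0.5, s = 0.525: f = 0 gives 0.525/0.5 = 1.050, and f = 0.5 gives 0.7625/0.75 = 1.017.

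| p | Expected treated, 10/p | Responders only: f = 0 | f = 0.25 | f = 0.5 | s | All treated: f = 0 | f = 0.25 | f = 0.5 |
|---|---|---|---|---|---|---|---|---|
| 0.3 | 33.3 | 3.33 | 2.11 | 1.54 | 0.322 | 1.073 | 1.034 | 1.017 |
| 0.5 | 20.0 | 2.00 | 1.60 | 1.33 | 0.525 | 1.050 | 1.030 | 1.017 |
| 0.7 | 14.3 | 1.43 | 1.29 | 1.18 | 0.720 | 1.029 | 1.019 | 1.012 |
| 0.9 | 11.1 | 1.11 | 1.08 | 1.05 | 0.908 | 1.009 | 1.007 | 1.004 |

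All entries are 1.00 when f = 1.

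**Step 4: compare with sampling error.** The 95% confidence half-width for a mean paired change, in SD of change, is t(0.975, n − 1)/√n. For n = 20, the expected total at p = 0.5, it is 2.093/4.472 = 0.47. For n = 10 it is 2.262/3.162 = 0.72. If the true all-treated change were 1 SD (an assumption), the 5.0% inflation at p = 0.5 and f = 0 would be 0.05 SD, about a ninth of the 0.47 half-width.

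**Step 5: are failures' readings available?** In Study Flow, impedance is recorded at each level before the biopsies there. If follow-up endoscopies use the same flow, a patient found on biopsy to have failed already has a post-treatment reading.

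**The case for a change.** The best case for a change is that the analysis set is undefined, the series is complete only when ten responders are in hand, and one sentence would settle the matter at no cost. The responder-only distortion could be large: 3.33 if 30% respond and failures do not change at all. The hypothesis supports the direction, although no data in the document show it. The arithmetic stands, and so does the observation that the set is not named. The document also leaves open how to count a patient who fails and later responds. It admits patients through "Those scheduled for clinically indicated upper endoscopy for esophageal biopsies either for initial diagnosis or activity assessment of EoE will be studied", so the analyst must check that a reading from an activity assessment really precedes the treatment under study.

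These are ordinary details of execution. The distortion needs two further steps that the plan does not take: dropping the failures, and presenting the remainder as all treated patients. Whether impedance recovers once eosinophilia clears is also a legitimate question for a mechanistic pilot. A responder-only result labelled as such would not be wrong, so insisting on the all-treated result as the main one is a matter of preference.

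The missing untreated EoE group is a separate limitation. It would be the same without the responder rule and is a fair trade-off in a pilot built on clinically indicated endoscopies. The Secondary Aim already speaks of changes following treatment, which is the accurate description. Regression to the mean is possible but indirect, because entry selects on eosinophil count and not on impedance.

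**Conclusion.** The concern does not call for a change. Read as worded, item 3 covers treated EoE patients with paired readings, failures included. On that reading the stopping rule inflates the mean change by 0.4% to 7.3% over response rates of 30% to 90% with failures changing between none and half as much as responders. That is small beside the sampling error of a series this size.

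The larger factors, 1.18 to 2.00 at response rates of 50% to 70%, apply only if the ten responders alone are analysed and the result is presented as that of all treated patients. All these figures rest on assumed response rates and relative changes, because the documents give neither. What remains is an unstated analysis set for a secondary endpoint in a pilot, which competent analysts would handle by reporting all paired patients, showing responders and failures separately, and giving the numbers treated and returned. The primary EoE-versus-control comparison does not depend on it.

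### The diagnostic cutoff is to come from the highest EoE and lowest control impedance, with no rule for overlap, no stated measurement level and no accuracy estimate

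*Combined protocol and SAP*

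**What the plan says.** The hypothesis sets the direction: "Patient with eosinophilic esophagitis have diminished mucosal impedance". EoE values should therefore lie below control values. The whole plan for a diagnostic cutoff is secondary endpoint 2: "Maximal mucosal impedance in EoE patients compared to minimal mucosal impedance in control patients to determine a potential diagnostic cutoff value".

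Study Design gives the group sizes: "a total of 75 patients with confirmed EoE patients" and "A total of 10 control patients will be studied". The Statistical Analysis section repeats the ten controls, but the only EoE number it gives is for the treatment comparison: "As a pilot, ten patients will be studied before and after treatment for eosinophilic esophagitis".

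Study Flow gives four readings per patient. Item 1 is buccal ("a baseline impedance will be obtained by asking the patient to hold the end of the probe against his/her buccal mucosa"), item 4 is esophageal at 5 cm above the gastroesophageal junction, and item 6 adds two levels: "The scope will then be withdrawn to 10 and 20 cm above the gastroesophageal junction and the same procedure including biopsies performed respectively".

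No section mentions sensitivity, specificity, an ROC curve, a confidence interval or validation.

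**The concern.** A maximum and a minimum point to a cutoff only when a gap lies between them. If the highest EoE value exceeds the lowest control value, the endpoint as written yields no cutoff, and the analyst must choose a rule after seeing the data. The choices then available differ greatly in accuracy.

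Two further gaps add to this. The endpoint does not say whether the extremes come from one level, from all levels pooled, from a per-patient summary or from the buccal site. It also asks for no estimate of accuracy, although its purpose is diagnostic. A reader would see a number but not how often it misclassifies patients. Because it rests on extremes, one bad probe contact could set that number.

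**Working it through.** The plan states no figure to reproduce. It gives no SD, effect size or target accuracy, so the separation *d* between group means, in SD units, is an assumption and is shown over a range.

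**Inputs from the documents:** 75 EoE patients, 10 controls, EoE lower; 10 v 10 as the alternative reading. **Assumptions:** one independent value per patient, EoE ~ N(0,1), controls ~ N(d,1), so AUC = Φ(d/√2).

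**1. Chance that the extremes do not overlap.** For n EoE patients and m controls,

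P = ∫ n φ(x) Φ(x)^(n−1) [1 − Φ(x − d)]^m dx

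| d | AUC | 75 v 10 | 10 v 10 |
|---|---|---|---|
| 2 | 0.92 | 0.1% | 9% |
| 2.33 | 0.95 | 0.7% | 18% |
| 3 | 0.983 | 9% | 48% |
| 4 | 0.998 | 55% | 87% |
| 5 | >0.999 | 92% | 98% |

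With 75 v 10 the chance reaches 5% only at d = 2.81 (AUC 0.977) and 50% at d = 3.90 (AUC 0.997).

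**2. What each candidate cutoff delivers.** The table gives mean true accuracy over simulated trials at d = 2.33, 75 v 10. J is sensitivity + specificity − 1.

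| Cutoff | Sensitivity | Specificity | J |
|---|---|---|---|
| EoE maximum | 99% | 48% (5th–95th percentile 19–71%) | 0.46 |
| Control minimum | 75% (about 40–95%) | 91% | 0.66 |
| Midpoint of the two | 93% | 75% | 0.69 |
| Empirical Youden | 88% | 84% (66–95%) | 0.72 |

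Two entries can be checked by hand. A new EoE patient falls below the maximum of 75 with probability 75/76 = 98.7%. A new control falls above the minimum of 10 with probability 10/11 = 90.9%.

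The in-sample J for Youden averages 0.83 against a true 0.72, so its apparent accuracy needs correction.

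**3. Effect of more data.** At 150 v 20, J falls to 0.38 for the EoE maximum and 0.61 for the control minimum. The midpoint (0.70) and Youden (0.73) do not degrade.

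**4. Effect of one aberrant reading** (hypothetical values, 75 v 10, d = 2.33).
- One EoE value 4 SD above the EoE mean moves the midpoint cutoff from 93%/75% to 99%/about 47–48%. Youden stays at 88%/84%.
- One control value 1 SD below the EoE mean sets the control-minimum cutoff at −1, so sensitivity is Φ(−1) = 16%. The midpoint becomes 75%/94% (J 0.70) and Youden 89%/82%.

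**5. Effect of the unstated level.** With d = 2.33 at each level and an assumed between-level correlation of 0.3 to 0.8, the chance of separation at 75 v 10 is at most about 0.01% with extremes over all three esophageal levels, 0.7% with one level, and 1.5–14% with the three-level mean.

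**6. Precision available from 10 controls.** If all 10 are classified correctly, the exact 95% lower bound on specificity is 0.025^(1/10) = 0.69. With 9 of 10 it is 0.55.

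**The case against.** The strongest reply is that this is a secondary, exploratory aim. The endpoint speaks only of a potential cutoff, the treatment comparison is called a pilot, no enrolment or treatment decision depends on the result, and an ROC analysis could be run later on the same readings. That limits the consequence, but a rule chosen later is still chosen after the data are seen.

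A second reply is that the case leans on 75 EoE patients. At 10 v 10 separation is more likely (48% at d = 3), and at d = 2.33 the midpoint has the same true J as Youden, 0.72. Even at 75 v 10 Youden gains only 0.03 over the midpoint and 0.06 over the control minimum. At d = 4 it is 0.925 against 0.918 for the midpoint. The midpoint's J also survives the aberrant control reading. All of this stands. But the plan does not specify the midpoint, so its good behavior does not rescue the endpoint as written.

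Third, the wording might mean a maximum or minimum within each patient across sites. It could, and the text does not settle it, which is a further ambiguity. Fourth, the missing level is not peculiar to this endpoint: primary endpoint 1 and secondary endpoint 3 do not name one either. That is correct and should be repaired for all three together.

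**Conclusion.** The concern holds and should be fixed. That the plan has no overlap rule, measurement level or accuracy estimate is a matter of reading the text and needs no assumption. The size of the problem does rest on assumptions: normal values, equal SD, one value per patient and a chosen d. On those, overlap is the likely outcome at 75 v 10 unless the AUC is about 0.997 or higher, and even at 10 v 10 it is more likely than not at AUC 0.983. When the groups overlap, specificity could be anywhere from about 48% to 91% depending on which extreme the analyst adopts. The argument rests on the undefined rule, the sensitivity to one reading and the absent accuracy estimate, not on the modest mean gain in J from Youden. The cutoff rule does not touch the primary comparison of EoE with controls.

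**What to change.** Replace secondary endpoint 2 with wording such as:

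*ROC analysis of one esophageal impedance value per patient (the mean of the 5, 10 and 20 cm readings), EoE against controls. We will report the AUC with a 95% CI, one cutoff chosen by the Youden index, and sensitivity and specificity at that cutoff with exact 95% CIs. Optimism will be corrected by bootstrap, reselecting the cutoff in each resample. The cutoff is exploratory and needs validation in other patients.*

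Add a tie rule, since under complete separation any value in the gap maximizes the index. State that with 10 controls even 10/10 correct gives a lower bound on specificity of only 69%. The group maximum and minimum can still be shown descriptively.

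The three-level mean and the equal weighting of errors in the Youden index are choices. The sponsor may prefer another single value or weighting, provided it is fixed before the data are seen. Name the reading for the other two endpoints at the same time. If a buccal cutoff is also wanted, analyze it separately.

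The cost is one paragraph and slightly more analysis, with no new patients, procedures or data. The downside is that the reported specificity will be visibly imprecise.

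### Secondary endpoint 2 seeks an EoE cutoff only against ten controls scoped for neither dysphagia nor GERD, so it cannot show specificity among patients with suspected EoE

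*Combined protocol and SAP*

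**What the plan says.** Secondary Endpoints, item 2, is the only diagnostic objective in the protocol: "Maximal mucosal impedance in EoE patients compared to minimal mucosal impedance in control patients to determine a potential diagnostic cutoff value".

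The controls are defined in the Inclusion criteria as "Patients undergoing clinically indicated upper endoscopy for indications other than dysphagia or GERD with normal appearing esophageal mucosa". Study Design and Statistical Analysis both put their number at ten. The EoE group is 75 confirmed patients, with dysphagia and at least 15 eosinophils per high-powered field despite a PPI trial of at least six weeks.

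Recruitment is wider than confirmed EoE. Study Design states: "Those scheduled for clinically indicated upper endoscopy for esophageal biopsies either for initial diagnosis or activity assessment of EoE will be studied". In Study Flow, step 4 is the reading ("The probe will be placed on the esophageal mucosa 5cm above the gastroesophageal junction for 5 seconds and recordings obtained") and step 5 the biopsy ("In patients with suspected or established EoE in whom clinically indicated esophageal biopsies are indicated, 2 biopsies will then be obtained at this level"). Step 6 repeats the sequence at 10 and 20 cm.

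On what else lowers impedance, the Background says that earlier work with this type of catheter "demonstrated lower mucosal impedance in areas of erosive esophagitis and in the mucosa of patients with nonerosive reflux disease compared to healthy controls". It also refers to "dilated intercellular spaces as has been observed in both gastroesophageal reflux and eosinophilic esophagitis".

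**The concern.** A diagnostic cutoff for EoE would be applied to patients in whom EoE is suspected. The question there is whether a low reading means EoE or something else that brings a patient to endoscopy. The Background names reflux disease as something else that lowers impedance, and the control definition leaves out patients scoped for GERD or dysphagia. The planned comparison therefore addresses EoE versus normal. It does not address EoE versus suspected but not EoE.

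The study will meet patients of the missing kind. Someone scoped for a first diagnosis has readings taken before the biopsy result is known. If the biopsies do not confirm EoE, that patient fits neither the EoE criterion nor, if scoped for dysphagia, the control criterion, and no endpoint uses the readings. What is at stake is whether any cutoff from endpoint 2 comes with evidence from the population it is meant for.

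**Working it through.** The plan gives 10 controls and 75 EoE patients without a calculation, so there is no figure to reproduce. The check traces who is measured and who is analysed, then asks what can be quantified.

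**Who is measured and who is analysed**

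- Confirmed EoE: measured; used in all three endpoints.
- Controls: measured; used in the primary endpoint and in endpoint 2.
- Suspected EoE, biopsy-negative: measured (steps 4 to 6); named in no endpoint, aim or analysis statement.

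Established EoE patients in histologic remission are a different group and can enter endpoint 3 as post-treatment cases.

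**What ten controls can show**

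Suppose the cutoff is the control minimum. The plan does not state this rule. Assume also exchangeable controls and one value per patient, although readings are taken at three levels and the plan does not say how they are combined.

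- All 10 of 10 controls are correctly classified by construction.
- True specificity in new controls of the same kind follows Beta(10, 1), with mean 10/11 = 0.909.
- The 2.5% point is 0.025^(1/10) = 0.692.
- For comparison, when all n are correct the lower bound is 0.025^(1/20) = 0.832 for n = 20 and 0.025^(1/40) = 0.912 for n = 40.

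These figures describe more people like the controls. They measure the small n and say nothing about the missing group.

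**What the missing group might do (illustration only)**

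Assume unit-SD normal readings and the same cutoff rule, with a fraction r of biopsy-negative suspected patients having readings s SD below normal because of reflux. Then

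expected specificity = (1 − r) × 0.909 + r × E(s),

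where E(s) = 0.815, 0.677 and 0.510 for s = 0.5, 1 and 1.5, by numerical integration.

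- r = 0.1, s = 0.5: 0.9 × 0.909 + 0.1 × 0.815 = 0.90
- r = 0.3, s = 1: 0.7 × 0.909 + 0.3 × 0.677 = 0.84
- r = 0.7, s = 1.5: 0.3 × 0.909 + 0.7 × 0.510 = 0.63
- r = 0: 0.909, no loss

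Neither r nor s is in the documents.

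**How many such patients**

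If a share p of those measured is confirmed, 75 confirmed cases imply 75 × (1 − p)/p who are not: 75, 32 or 8 for p = 0.5, 0.7 or 0.9. The share is assumed, and established patients among the 75 would lower these numbers. With an observed specificity of 80%, the exact 95% interval is 69–88% for n = 75, 61–92% for n = 30 and 44–97% for n = 10.

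**Whether endpoint 2 would yield a cutoff at all**

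With normal readings, equal SD and an EoE mean d SD below controls, the probability that all 75 EoE values lie below all 10 control values is ∫ 75 φ(x) Φ(x)^74 [1 − Φ(x − d)]^10 dx. This is 0.001 for d = 2, 0.091 for d = 3 and 0.55 for d = 4. For d of 2 or 3 the two extremes would usually cross and fix no single value.

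**The case against.** The strongest reply is that diagnostic accuracy is not an aim of this study. The Aims concern impedance in EoE and its change with treatment. Endpoint 2 is secondary and tentatively worded, and it promises no sensitivity, specificity or clinical use. Comparing confirmed cases with people free of esophageal disease is a defensible first step. Biopsy-negative patients may simply be ineligible after measurement, and a group made from them would have unknown size, mix and PPI exposure. This stands as an argument about weight: the point is minor. It does not close the gap, because the endpoint still names a diagnostic purpose and the plan has no data on patients with suspected disease who turn out not to have EoE. Calling them ineligible explains why their readings go unused.

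A reader might infer more than the documents support:

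- **That the study will report a cutoff with overstated specificity.** The plan states no rule for placing the cutoff, and under the assumptions above the two extremes may fix none.
- **That 91% and 69% measure the harm from the missing group.** They measure only the effect of having ten controls.
- **That specificity in suspected patients would fall to 63%.** That rests wholly on an assumed reflux fraction and an assumed drop; with no reflux there is no loss.
- **That the primary comparison is undermined.** It asks whether EoE differs from normal, and these controls suit that question.

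**Conclusion.** The point holds in limited form. Endpoint 2 can distinguish EoE from normal but cannot show the specificity of a cutoff among patients with suspected EoE, and readings from biopsy-negative suspected patients are left without a role. This follows from the group definitions, the order of Study Flow and the Background's statements on reflux; it needs no distributional assumption.

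Its size cannot be derived: the documents give neither the impedance distribution in suspected patients nor their number. The conditional 91% (lower bound 69%) requires the control-minimum rule, exchangeable controls and one value per patient. The consequence is confined to one secondary endpoint that the plan itself presents as tentative, so this is a cheap improvement and not a defect in the main design.

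**What to change.** - Amend the eligibility wording so that suspected-EoE patients with no prior EoE diagnosis and fewer than 15 eosinophils per high-powered field at the study endoscopy form a second, exploratory comparison group. Record their PPI exposure.
- For endpoint 2, report the sensitivity and specificity of any candidate cutoff, with confidence intervals, for EoE against this group alongside EoE against the existing controls.
- Label a cutoff based on the existing controls alone as EoE-versus-normal only.
- Keep the existing controls as the reference for normal, and leave the primary comparison as it is.

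The cost is an eligibility amendment, one analysis paragraph and one data field, with no new procedure. There are three downsides. Specificity may look less favourable. The group may be small, and its size cannot be predicted from the documents. Its PPI exposure may differ from that of the EoE group, which would complicate interpretation.
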